7.7 EXTENT OF EXPOSURE

The number of subjects who received a dose of randomized trial drug will be tabulated. The duration of infusion [in minutes] and the amount of treatment received [mg] will be summarised by descriptive statistics (N, mean, SD, minimum, Q1, median, Q3, maximum) on Day 1.

The number and percentage of patients according to the duration of infusion will also be classified according to the following categories:

Duration of infusion [min] categories

- Duration "< 60 min",
- Duration ">=60 min to < 120 min",
- Duration ">=120 min to < 240 min",
- Duration ">= 240 min".

The above will also be summarized for the open-label treatment with Spesolimab provided on Day 8, as well as for the rescue treatment with Spesolimab.

7.8 SAFETY ANALYSIS

All safety analyses will be performed based on the SAF following BI standards. No hypothesis testing is planned.

Primary analysis for safety data

The primary safety analysis will be done based on data through the first 12 weeks of treatment (i.e., up to Day 85)).

In the primary safety analysis, OC-IE method will be used whereby data after actual time of intake of (optional) open-label Spesolimab on Day 8, or rescue medication with Spesolimab for treatment of a GPP flare will be censored for reporting.

Since the onset time of an AE will not be collected in the trial, any AE which occurs on the same day as the first dose of randomized trial medication (Day 1) will be, conservatively, assigned to the on-treatment period. Any AE which occurs on the same day as the first dose of a non-randomized Spesolimab medication administration (i.e. for OL D8, or for rescue) will be assigned to the period commencing on the day of use of the non-randomized Spesolimab treatment. For safety assessments by visits (except for local tolerability or post-treatment vital signs), if time is not collected, data on the same day of (optional) open-label Spesolimab on Day 8, or rescue medication with Spesolimab for treatment of a GPP flare will not be excluded.

In addition, all AE tables will be repeated up to Week 1 and up to the end of REP of the randomized treatment at Day 1 respectively.

Further analysis for safety data

In further analysis of safety data, AEs of patients will be reported by treatments and their starting time periods relative to the use of randomized treatment at Day 1, OL Spesolimab at Day 8 and rescue medication with Spesolimab (see [Section 6.1](#)). That is to say, one patient may be counted in multiple treatment periods as defined below based on the use of randomized treatment at Day 1, OL Spesolimab at Day 8 and rescue medication with Spesolimab. In addition, AEs of patients post any use of randomized or non-randomized Spesolimab are summarized where two arms will be pooled:

- **“Prior non-rand. Speso”** (i.e. TEAE starting before use of any non-randomized Spesolimab are considered)
- **“Post OL Speso at D8”** (i.e. TEAE starting post OL dose at Day 8 but before rescue medication with Spesolimab if applicable are considered)
- **“Post rescue with Speso”** (i.e. TEAE starting post rescue medication with Spesolimab are considered)
- **“Post any Speso”** (i.e. TEAE starting post any randomized or non-randomized Spesolimab are considered where two arms will be pooled)

Descriptive summaries of all AE and potentially clinically significant abnormal Lab values will be repeated up to the end of REP of any of randomized treatment at D1 or non-randomized Spesolimab.

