Tabulations of frequencies for categorical data will include all possible categories and will display the number of observations in a category as well as the percentage (%) relative to the

respective treatment. Percentages will be rounded to one decimal place. The category missing will be displayed if and only if there actually are missing values. Percentages will be based on all patients in the respective patient set whether they have non-missing values or not.

Disposition of the patient population participating in the trial will be summarized by the presentation of the frequency of patients screened, randomized, screened but not randomized, randomized but not treated, randomized and treated, who completed trial medication (on Day 1), who were prematurely discontinued from trial medication (on Day 1), by reason, who completed participation in the trial, who were prematurely discontinued from trial, by reason, and who entered the extension trial 1368.25.

The frequency of patients with iPDS, also summarized by whether or not the iPD led to exclusion from the PPS, will be presented. The frequency of patients in each of the different analysis sets will also be presented.

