7.8.1 Adverse events

AEs will be coded with the most recent version of MedDRA. Patients will be analyzed according to the actual treatment received.

The exposure adjusted incidence rate (per 100 subject years) of a selected treatment emergent adverse event is defined as the number of subjects experiencing the adverse event per treatment group during time at risk divided by the total time of subjects at risk in that treatment group to contribute the event to the analysis multiplied by 100 (per 100 subject years).

Incidence rate [1/100 Subject years (pt-yrs)] = $100 * \frac{\text{number of subjects with AE}}{\text{Total AE-specific time at risk [subject years]}}$.

For analysis up to Week 1, Week 12 and the end of REP of randomized drug:

Time at risk [subject years] = (date of onset of TEAE up to the end time of risk – randomized study drug start date + 1) / 365.25

The end time of risk will be the min (day of death, randomized drug stop date + X days, the day prior to OL Spesolimab at Day 8, the day prior to rescue medication with Spesolimab, the day prior to first dose in the extension study if patient will be rolled over or last contact date

per EoS page if patient will not be rolled over). Here X equals to 6, 84 and 112 for analysis up to Week 1, Week 12 and the end of REP of randomized drug respectively.

For the further analysis on safety data,

Time at risk prior to non-randomized Spesolimab/ post OL Spesolimab at Day 8/post rescue medication with Spesolimab [subject years] = (date of onset of TEAE up to the end time of risk – randomized treatment date/Day 8 / date of rescue use of Spesolimab + 1) / 365.25

End of time at risk prior to any non-randomized Spesolimab will be the min of (Day 113 or the day prior to any non-randomized Spesolimab, last contact date per EoS page if patient will not be rolled over or the day prior to first dose in the extension study if patient will be rolled over).

End of time at risk post OL Spesolimab at Day 8 will be the min of (Day 8 Spesolimab date +112 or the day prior to the use of rescue medication with Spesolimab or the last contact date per EoS page if patient will not be rolled over or the day prior to first dose in the extension study if patient will be rolled over).

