End of time at risk post use of rescue medication with Spesolimab will be the min of (the day of rescue medication with Spesolimab in the trial +112 or the last contact date per EoS page if patient will not be rolled over or the day prior to first dose in the extension study if patient will be rolled over).

In addition, for overall period post use of any Spesolimab,

Time at risk overall post use of any Spesolimab [subject years] = (date of onset of TEAE up to the end time of risk – first use of any Spesolimab start date + 1) / 365.25

End of time at risk for overall post use of any Spesolimab will be min of (the day of last Spesolimab in the trial +112 or the last contact date per EoS page if patient will not be rolled over or the day prior to first dose in the extension study if patient will be rolled over).

The analyses of AEs will be descriptive in nature. All analyses of AEs will be based on the exposure adjusted incidence rates (per 100 subject years), as well as the number of patients with AEs and not on the number of AEs. System organ classes (if applicable) will be sorted according to the standard sort order specified by the EMA, preferred terms (if applicable) will be sorted by total frequency (within system organ class) across all treatment columns, cf. [Section 6.1](#).

For further details on summarization of AE data, please refer to "Handling and summarization of adverse event data for clinical trial reports and integrated summaries" ([7](#)) and "Handling of missing and incomplete AE dates" ([4](#)).

The analysis of AEs will be based on the concept of treatment emergent AEs. This means that all AEs will be assigned to the screening phase, treatment phase or follow-up phase as

defined in [Section 6.1](#). Since only the start date of an AE is collected (without start time), any AE occurrence on the same day as randomized Spesolimab/placebo administration will be assigned to the on-treatment period.

An overall summary of AEs will be presented. This overall summary will include summary for the class of AESIs.

The following are considered as AESIs ([see Sec 5.2.6.1 of CTP](#)):

- Hepatic injury
- Systemic hypersensitivity reactions including Infusion reactions and anaphylactic reaction
- Severe infections (according to RCTC grading in the ISF)
- Opportunistic and mycobacterium tuberculosis infections

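### The Day 85 and REP adverse-event tables stop counting at open-label or rescue spesolimab, so their percentages are not comparable between arms and their pooled rates need a caveat

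*SAP*

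**What the plan says.** **Horizon and censoring.** SAP 7.8: "The primary safety analysis will be done based on data through the first 12 weeks of treatment", that is, to Day 85. It continues: "In the primary safety analysis, OC-IE method will be used whereby data after actual time of intake of (optional) open-label Spesolimab on Day 8", or of rescue spesolimab, are censored for reporting. Protocol 7.3.5 likewise leaves such data out of displays by planned treatment.

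**Time at risk.** In SAP 7.8.1 the end of risk is the earliest of several dates, including "the day prior to OL Spesolimab at Day 8, the day prior to rescue medication with Spesolimab". For the three horizons: "Here X equals to 6, 84 and 112 for analysis up to Week 1, Week 12 and the end of REP". Counting from Day 1, these end on Days 7, 85 and 113. Protocol 7.3.5 instead censors a patient without the AE on the date of the open-label or rescue dose itself.

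**What is reported.** SAP 7.8.1: "All analyses of AEs will be based on the exposure adjusted incidence rates (per 100 subject years), as well as the number of patients". SAP 7 adds: "Percentages will be based on all patients in the respective patient set whether they have non-missing values or not".

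**Other planned displays.** SAP 7.8: "In addition, all AE tables will be repeated up to Week 1 and up to the end of REP" of the randomised treatment. AEs after a non-randomised dose go to separate post-open-label and post-rescue summaries, and to a combined one: "TEAE starting post any randomized or non-randomized Spesolimab are considered where two arms will be pooled".

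**Who gets open-label drug.** Under protocol 3.1, eligibility at Day 8 needs no earlier escape treatment, a GPPGA of at least 2 and a pustulation subscore of at least 2. Escape treatment does not end safety follow-up (the OC-IE definition in SAP 6.6.3).

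**The concern.** A patient given open-label spesolimab at Day 8 contributes 7 days to the randomised-arm tables. A patient given neither open-label nor rescue drug can contribute 85 days, or up to 113 in the residual effect period (REP) tables. The open-label dose depends on outcome, and the protocol plans for Week 1 response of 10% on placebo and 60% on spesolimab. Placebo follow-up is therefore likely to be the shorter.

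The two planned measures can then mislead in opposite directions. The percentage keeps short-follow-up patients in its denominator and so understates placebo. The exposure-adjusted rate cuts events and time together, but if AEs cluster in the flare week, the arm with less late follow-up shows the higher rate. The visible SAP text states neither limit and does not say which table should carry the comparison between arms. Global Amendment 1 raised the sample size partly to strengthen the safety database, so a clear reading of the tables labelled primary matters.

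**Working it through.** **Plan's own figures.** The documents give no AE rate, person-time or open-label share to reproduce. The arm sizes and response rates used here do reproduce the stated power for the primary endpoint: exact enumeration of the Z-pooled test at 0.6 v 0.1 with 34:17 gives 96.28%, against 96.3% in protocol Table 7.7:1.

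**Inputs from the documents.** 17 placebo and 34 spesolimab patients; last days at risk 7, 85 and 113; planned response 10% and 60% (protocol 7.7). If every non-responder took open-label drug, use would be 90% and 40%.

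**Assumptions.** Open-label use (placebo/spesolimab) of 90/40, 75/25, 60/20 and 50/30, with 50/50 as a control. AE hazard h1 on Days 1-7 and h2 from Day 8, the same in both arms. Later rescue, dropout and rollover to the extension are ignored.

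**Formulas.** A share p is censored after Day 7; the rest run L further days (78 to Day 85, 106 to Day 113).

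- S1 = exp(-7 h1); E1 = 1 - S1; E2 = (1 - p) S1 [1 - exp(-L h2)]
- Percentage with an AE = E1 + E2
- T1 = E1/h1; T2 = E2/h2; rate per 100 patient-years = 36,525 (E1 + E2)/(T1 + T2)
- Maximum mean days at risk = 7 + (1 - p)L
- Gap in percentages = (p placebo - p spesolimab) S1 [1 - exp(-L h2)], which is zero when open-label use is equal

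**Worked percentage, 90/40, constant 0.01 per day, Day 85.** S1 = 0.9324, E1 = 0.0676, 1 - exp(-0.78) = 0.5416.

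- Placebo: 0.0676 + 0.1 x 0.9324 x 0.5416 = 11.8%
- Spesolimab: 0.0676 + 0.6 x 0.9324 x 0.5416 = 37.1%

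**Worked rate, 90/40, 0.05 then 0.01 per day.** S1 = 0.7047, E1 = 0.2953, T1 = 5.91 days.

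- Placebo: E2 = 0.0382, T2 = 3.82; rate = 36,525 x 0.3335/9.72 = 1,253
- Spesolimab: E2 = 0.2290, T2 = 22.90; rate = 36,525 x 0.5243/28.81 = 665
- Ratio 0.53

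**Day 85 results, placebo v spesolimab, no drug effect**

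| Open-label use | Max. mean days at risk | % with AE, 0.005/day | % with AE, 0.01/day | Rate ratio, constant hazard | Rate ratio, 0.05 then 0.01 |
|---|---|---|---|---|---|
| 90/40 | 14.8 v 53.8 | 7 v 22 | 12 v 37 | 1.00 | 0.53 |
| 75/25 | 26.5 v 65.5 | 11 v 27 | 19 v 45 | 1.00 | 0.67 |
| 60/20 | 38.2 v 69.4 | 16 v 28 | 27 v 47 | 1.00 | 0.78 |
| 50/30 | 46.0 v 61.6 | 19 v 25 | 32 v 42 | 1.00 | 0.89 |
| 50/50 | 46.0 v 46.0 | 19 v 19 | 32 v 32 | 1.00 | 1.00 |

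The unrounded gaps run from 6.2 points (50/30, 0.005/day) to 25.2 points (90/40 and 75/25, 0.01/day).

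**REP tables to Day 113, constant 0.01 per day.** 13% v 43% (90/40), 22% v 52% (75/25) and 31% v 56% (60/20). Rollover to the extension can end risk earlier, so actual follow-up may be shorter than this.

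**Effect of splitting time, 75/25, 0.05 then 0.01.** The pooled rates of 924 v 615 become 1,826 v 1,826 for Days 1-7 and 365 v 365 from Day 8. Expected patients with a first AE are 5.0 v 10.0 and 1.6 v 9.7.

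**Week 1 tables.** These end on Day 7, before any open-label dose. They hold at most 17 x 7 = 119 v 34 x 7 = 238 patient-days.

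**The case against.** **Most of the analysis is already planned.** Week 1 tables, exposure-adjusted rates and separate summaries after each non-randomised dose are all specified, and nothing is tested. This stands. What is missing is a statement of limits, a named table for the between-arm reading, and time at risk shown by arm. A reader might infer that AEs after open-label drug are lost or hidden. The documents do not support that: patients stay in the trial and those AEs are reported in the later-period and pooled summaries.

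**The size rests on assumed open-label use.** This also stands. A reader might take 90/40 as the expected use. It is only a per-arm ceiling under the planned response rates: a non-responder with a pustulation subscore of 1 does not qualify, and a patient who took escape treatment is not eligible. SAP 7.5.2 expects most placebo patients to take escape medication by Day 8 or open-label drug at Day 8, but escape does not end safety follow-up, so more escape on placebo narrows the gap. Nor is 90/40 a bound on the contrast, because spesolimab use below 40% would widen it.

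**The model is simple.** Open-label and other patients share one hazard here, although open-label patients have a persisting flare and worsening of the underlying disease is recorded as an AE (protocol 5.2.6.2). The figures isolate unequal follow-up and do not measure informative censoring.

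**Week 1 is a thin comparison.** It has few events, includes AEs after escape treatment, and cannot speak to late AEs of a drug with a half-life of about 4 weeks. This limits what the Week 1 tables can show, but it does not make the Day 85 percentages comparable.

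**Some text is not visible.** Redacted SAP sections and the sponsor's AE guideline may already require time at risk to be printed.

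**Conclusion.** The point holds as a minor one. If open-label use is higher on placebo, the Day 85 and REP percentages are not comparable between arms: with equal hazards they run against spesolimab, by about 6 to 25 points at Day 85 in the assumed constant-hazard cases. Pooled rates are unbiased only with a constant hazard and non-informative censoring. With a high Week 1 hazard they run the other way, at about 0.53 to 0.89. Neither distortion from unequal follow-up arises if open-label use is equal.

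A reader might conclude that the censoring rule is wrong, or that the plan has no usable between-arm safety comparison. Neither follows. The rule keeps AEs after non-randomised spesolimab out of the randomised-arm columns, and the Week 1 tables avoid this censoring. Open-label shares and hazards are assumptions throughout. No hypothesis test or efficacy result is touched.

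**What to change.** Keep the censoring rule and amend SAP 7.8 and 7.8.1:

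1. Name the planned Week 1 tables as the between-arm AE comparison. State that they include AEs after escape medication, cover at most 119 v 238 patient-days, and say nothing about late AEs.
2. Print total time at risk per arm in the Day 85 and REP tables. For the overall AE summary and the main categories (any AE, SAE, AESI), give rates separately for Days 1-7 and Day 8 onward, using the first-event risk set: a patient whose first such AE falls in Days 1-7 leaves the later risk set. If maximum-intensity tables are split, derive the counts directly; subtracting Week 1 from Week 12 fails when a patient's worst grade changes.
3. Footnote that pooled Day 85 and REP percentages are not comparable between arms, that pooled rates assume a constant hazard and non-informative censoring, and that the Day 8 onward columns are a non-randomised description.
4. Reconcile the end of risk in protocol 7.3.5 (date of the dose) with SAP 7.8.1 (day before), a one-day difference.

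The cost is wording and a little programming; no new data are needed. The drawback is that Week 1 will hold few events: at 0.005 per day, 0.6 v 1.2 expected patients with an AE; at 0.03 per day, 3.2 v 6.4. Escape use can also shift Week 1 slightly. If 20% v 5% take escape from Day 4 and it doubles a 0.03 per day hazard (assumed), Week 1 shows 20.8% v 19.4%.

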²Should a patient prematurely discontinue from the treatment, every effort should be made to keep the patient in the trial and complete all of the remaining study visits. If this is not possible, assessments at V9 (Wk1), V12 (Wk4), and EoS (V14 or V15 or V16 as applicable) should be completed or at a minimum an early EoS visit.

³If a patient qualifies for rescue treatment with open label BI 655130 at either a scheduled or unscheduled visit from after Day 8 and up to and including Week 12, all procedures/measurements listed for V9 (with the exception of skin biopsy, Whole Blood for RNA sequencing, Soluble Protein Biomarkers in Serum and Whole Blood for Flow Cytometry) are to be performed prior to dosing and an IRT call is to be placed prior to dosing.

⁴ C = Complete Physical Examination; T = Targeted physical examination. Refer to [Section 5.2.1](#) for additional details.

Clinical Trial Protocol

Proprietary confidential information © 2020 Boehringer Ingelheim International GmbH or one or more of its affiliated companies

⁵Per physician's assessment, Days 4 through 7 are optional if the patient has achieved complete pustular clearance (GPPGA pustulation sub score = 0) at the prior visit.

⁶Informed consent will be signed at the screening visit (V1). For patients completing V1 and V2 > 6 weeks apart, it is recommended that the patient is asked to re-confirm (verbally) his/her consent to participate in the trial at Visit 2.

⁷Infection testing includes tuberculosis, hepatitis B, hepatitis C, and HIV assessments (see [Table 5.2.3: 1](#)). EoS infection testing should only be done once at V14 or V15 or V16 as applicable.

⁸These procedures do not need to be repeated/Performed when V1 and V2 are performed on the same day.

⁹IL36RN mutation status is to be obtained from the patient's historical data if available.

¹⁰Vital signs: a) On non-study-drug administration days, vital sign assessments are to be done prior to blood sampling; b) On study drug administration days, vital signs will be assessed at pre-dose, at approximately 5 minutes after the end of infusion, and 120 mins after the end of infusion.

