5.2.6.2 Adverse event collection and reporting

AE Collection

The Investigator shall maintain and keep detailed records of all AEs in their patient files.

The following must be collected and documented on the appropriate CRF(s) by the investigator:

For patients rolling over into open label extension trial (1368-0025):

- From signing the informed consent of the parent trial onwards until the first dose of trial medication in the extension trial:
 - all AEs (non-serious and serious) and all AESIs.

For patients not rolling over into subsequent OLE trial (1368-0025):

- From signing the informed consent onwards until the individual patient's end of trial:
 - all AEs (serious and non-serious) and all AESIs.
- After the individual patient's end of trial:
the investigator does not need to actively monitor the patient for AEs but should only report related SAEs and related AESIs of which the investigator may become aware of by any means of communication, e.g. phone call. Those AEs should be reported on the BI SAE form, but not on the CRF.

The follow-up period describes the period of time from the last administration of trial medication until the end of trial examination (last per-protocol contact).

AE reporting to sponsor and timelines

The investigator must report SAEs, AESIs, and non-serious AEs which are relevant for the reported SAE or AESI, on the BI SAE form via fax immediately (within 24 hours) to the sponsor's unique entry point (country specific contact details will be provided in the ISF).

Proprietary confidential information © 2020 Boehringer Ingelheim International GmbH or one or more of its affiliated companies

The same timeline applies if follow-up information becomes available. In specific occasions the investigator could inform the sponsor upfront via telephone. This does not replace the requirement to complete and fax the BI SAE form.

With receipt of any further information to these events, a follow-up SAE form has to be provided. For follow-up information the same rules and timeline apply as for initial information.

Information required

For each AE, the investigator should provide the information requested on the appropriate eCRF pages and, if applicable, the BI SAE form. The investigator should determine the causal relationship to the trial medication.

The following should also be recorded as an (S)AE in the CRF and, if applicable, BI SAE form:

- Worsening of the underlying disease or of other pre-existing conditions

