7.3.5 Safety analyses

Adverse events will be coded using the current version of Medical Dictionary for Regulatory Activities (MedDRA) coding dictionary. Standard BI summary tables and listings will be produced.

All treated patients will be included in the safety analysis. In general, safety analyses will be descriptive in nature and will be based on BI standards. No hypothesis testing is planned. Statistical analysis and reporting of adverse events will concentrate on treatment-emergent adverse events. To this end, all adverse events occurring between start of treatment and end of the residual effect period will be considered 'treatment-emergent'; the residual effect period (REP) is defined as 16 weeks after the last dose of trial medication. Note that for patients who continue into the extension trial, TEAE up to the first dose in the extension trial will be available for display in the current study. Adverse events that start before first drug intake and deteriorate under treatment will also be considered as 'treatment-emergent'. For all subjects who received OL BI 655130 at D8 or rescue medication with BI 655130, safety assessments including adverse events, laboratories, vital signs etc. which occurred subsequent to such intake will be excluded from presentations according to the planned treatments; these data will, however, be included in summaries where all data after any use of BI 655130 are displayed.

Frequency, severity, and causal relationship of adverse events will be tabulated by system organ class (SOC) and preferred term after coding according to the current version of the MedDRA.

The exposure adjusted incidence rate (per 100 subject years) of a selected treatment emergent adverse event is defined as the number of subjects experiencing the adverse event per treatment group during time at risk divided by the total time of subjects at risk in that treatment group to contribute the event to the analysis multiplied by 100 (per 100 subject years), where:

[figure not shown]
$$\text{Time at risk [subject years]} = (\text{date of onset of TEAE} - \text{study drug start date} + 1) / 365.25$$

[figure not shown]

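### A flare recurrence recorded as an AE on the day of rescue spesolimab is counted after the rescue dose it prompted and drops out of the preceding period

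*SAP*

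**What the plan says.** **SAP 7.8.** The primary safety analysis censors "data after actual time of intake of (optional) open-label Spesolimab on Day 8, or rescue medication with Spesolimab". The same section then sets a tie-break for AEs. It begins "Since the onset time of an AE will not be collected in the trial", and an AE on the day of a non-randomised spesolimab dose "will be assigned to the period commencing on the day of use of the non-randomized Spesolimab treatment". No exception is written for the event that led to the dose.

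**SAP 7.8.1.** For the randomised-drug tables, the end of time at risk is a minimum that includes "the day prior to OL Spesolimab at Day 8, the day prior to rescue medication with Spesolimab". The post-open-label period likewise ends the day before rescue.

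**Protocol 5.2.6.2.** Among the items to be recorded as an (S)AE is "Worsening of the underlying disease or of other pre-existing conditions".

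**Protocol Table 3.1:1 and Flow Chart footnote 3.** Rescue requires a rise of at least 2 points in GPPGA with a pustulation subscore of at least 2, after an earlier GPPGA of 0 or 1. At a rescue visit the V9 procedures, with a few sampling exceptions, "are to be performed prior to dosing and an IRT call is to be placed prior to dosing". Those procedures include GPPGA and the adverse-event row.

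**Protocol 7.3.5.** For patients given such a dose, safety data "which occurred subsequent to such intake will be excluded from presentations according to the planned treatments". For a patient without the event, time at risk is censored at the date of rescue medication itself.

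**The concern.** The tie-break is reasonable when the order of AE and infusion on one day is unknown. For the flare that justified a rescue dose, the order is known: the flare has to be present and scored before the drug is given. If its AE onset is dated that day, three things follow.

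- The *Post rescue with Speso* table shows it as an event following the dose. If the flare led to hospital admission, this is a misplaced SAE.
- It leaves the preceding period: the randomised-arm Week 12 and residual-effect-period tables, or the post-open-label period if a Day 8 dose was given.
- For a placebo patient with no earlier spesolimab, it is counted as following spesolimab although none had been received.

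With arms of 34 and 17, one patient is 2.9% (1/34) or 5.9% (1/17) of a column, so a few shifted events would be visible.

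**Working it through.** The plan states no figure on this point, so there is nothing to reproduce. The check applies the day rules, then gives an illustration.

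**1. Day arithmetic for rescue on Day D.** SAP time at risk is (end date − start date + 1).

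- Preceding period in a patient with no Day 8 dose and no event: ends on Day D−1, giving (D−1) − 1 + 1 = D−1 days. For D = 57 this is 56 days.
- AE dated Day D: counted post-rescue with D − D + 1 = 1 day at risk.
- AE dated Day D−1 or earlier: stays in the preceding period.
- Protocol 7.3.5 censors at Day D: D − 1 + 1 = 57 days for D = 57. The SAP stops one day short of this. The readable part of SAP Section 4 does not list the change; part of that section is redacted.

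So the shift equals the number of rescue-triggering flares with AE onset dated on the dosing day.

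**2. The rule against the other texts.**

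- Protocol 7.3.5 excludes events subsequent to intake. A triggering flare is not one.
- The SAP 7.8 censoring principle refers to the actual time of intake. A triggering flare precedes it.
- The SAP 7.8 label for the period before non-randomised drug covers TEAEs that start before its use. A triggering flare meets that definition but is filed elsewhere.
- For by-visit safety data other than local tolerability and post-treatment vital signs, the same SAP paragraph does the opposite: same-day values without a recorded time are kept.
- SAP 6.6.3 sets a missing rescue date to the date of the flare. That creates a same-day match whenever the AE carries the flare date.

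**3. Size, on assumptions.** The documents give no count of rescues and no rate of same-day dating. Assume 34 patients, 4 rescued on Day 57, everyone else at risk to Day 85 (randomised drug stop date + 84 days), and flares not dated on the dosing day dated Day 56. Rate = 100 × patients with the AE / years at risk.

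- Years at risk under the SAP rule: (30 × 85 + 4 × 56) / 365.25 = 2774 / 365.25 = 7.595.
- No flare dated on the dosing day: 100 × 4 / 7.595 = 52.7.
- Two of four: 100 × 2 / 7.595 = 26.3.
- All four: 0.
- All four, but kept in the preceding period with risk ending on Day 57: (30 × 85 + 4 × 57) / 365.25 = 7.606 years, and 100 × 4 / 7.606 = 52.6.

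The extra day at risk is immaterial. The loss from the numerator is what counts.

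**4. Day 8 open-label dose.** Under Table 3.1:1 this dose needs GPPGA of at least 2 and pustulation of at least 2 at Week 1. It treats a persisting index flare that began before Day 1 and requires no new worsening. The rule reaches it only if a GPP worsening is recorded with onset on Day 8, before the dose. The Week 1 AE table is untouched in any case: "Here X equals to 6, 84 and 112 for analysis up to Week 1, Week 12", and Day 1 + 6 is Day 7.

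**The case against.** The SAP needs some rule when onset times are missing, and this one is cautious. Both non-randomised doses are spesolimab, so same-day events are charged to the experimental drug, which matches the Day 1 rule. That holds for infusion reactions and for most AEs. It does not hold for an event that had to exist before the dose could be given.

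The rule works on the AE onset date, which Protocol 8.3.1 makes mandatory. Footnote 3 fixes the order of procedures at the visit, not the onset date of the flare. A flare dated a day or more before rescue stays where it belongs. This stands: a reader might infer that every triggering flare is moved, and the documents do not support that.

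The events also remain visible elsewhere. Individual values are listed (SAP 7), and SAP 6.7 refers to an analysis of flare recurrence that is not based on visits. Rescue use is summarised separately under SAP 7.6.3, whose text is not in the public copy. In patients randomised to spesolimab the flare still appears in the pooled table after any spesolimab. Safety is descriptive, with no hypothesis tests. These points limit the consequence but do not correct the AE tables.

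**Conclusion.** The point holds for a rescue-triggering flare recorded as an AE with onset on the dosing day. Such an event is counted after the dose it preceded, against Protocol 7.3.5 and the SAP's own period definition. The number affected runs from zero to all rescue-triggering flares, and the rates in the illustration rest on assumed counts. It is a small defect in descriptive tables that is cheap to repair.

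Two stronger readings are tempting, and the documents support neither.

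- *The rule flatters the spesolimab arm.* Planned Week 1 GPPGA 0/1 rates of 60% and 10% imply 34 × 0.60 = 20.4 and 17 × 0.10 = 1.7 responders to randomised drug, so removals might seem to fall mainly on spesolimab. But Table 3.1:1 also allows rescue after a response to escape medication, and SAP 6.6.3 keeps data after escape in the randomised-arm safety display. The placebo pool is therefore larger by an unknown amount, and no direction is established.
- *All Day 8 open-label recipients are affected.* Receiving that dose does not imply an AE dated Day 8.

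**What to change.** In SAP 7.8 and 7.8.1, state that an AE of GPP worsening or flare recurrence that was the reason for a non-randomised spesolimab dose, and has onset on the dosing day, is assigned to the preceding period. Time at risk for that AE then ends on the dosing day, in line with the censoring date in Protocol 7.3.5. Keep the present rule for all other same-day AEs. As a check, tabulate same-day flare AEs both ways. Record the change in SAP Section 4.

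The cost is one sentence and one programming rule on preferred term, onset date and dosing date. Which same-day AEs were the reason for the dose can be settled at the report planning or database lock meeting, before unblinding. The downside is that a true worsening later on the same day, after the infusion, could be counted before it. For a placebo patient that would place it in the placebo column. The two-way display shows how much depends on this.
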